## 3. STUDY DESIGN

### **3.1 General Design**

This is a prospective, open-label, randomized, pilot study of reprogramming therapy in patients with recurrent PCa based on rising PSA only. Reprogramming therapy will include 5-azacitidine and all-trans retinoic acid. Expected duration of subject participation is 24 months.

All study will be assigned in a 1:1 randomization using computer random number generator to either the '5-AZA+ATRA' group or the 'no therapy' group. All enrollees will receive Leuprolide 7.5 mg x 1 on Day 1. On Day 29, they will initiate treatment phase 1. During this phase, patients in the '5-AZA + ATRA' group will receive treatment on a 28-day cycle, in the absence of prohibitive toxicities, for 3 cycles. During treatment phase 2, the 'no therapy' group will receive 5-AZA + ATRA on a 28-day cycle, in the absence of prohibitive toxicities, for 3 cycles. The treatment effect will be determined via comparing the intra-individual disease progression outcome at the end of the treatment phase 1, with period effect being separated through randomization. After treatment phase 1 and phase 2, all patients will be followed for a total of 24 months from the start of the study or until the events leading to discontinuation as outlined in Section 7.1 are observed. 5-AZA will be given subcutaneously on days 1-5 at a dose of 40 mg/m^2. ATRA, dosed at 45 mg/m^2 daily (divided into 2 doses), will be taken orally on days 3-7 of each cycle.

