### *Follow Up Period:*

Patients will be assessed with physical examination, AE monitoring, and laboratory values. CT abdomen/pelvis and bone scan assessments will be performed as deemed appropriate by the clinical investigator. Patients will continue with follow up for total of 24 months from day 1 of study, unless there is evidence of radiographic progression and/or initiation of other cancer-directed therapies.

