### **8.2 Sample Size and Accrual**

The primary endpoint is disease progression free rate at the end of treatment phase 1. Disease progression is defined as either PSA progression or radiographic progression relative to baseline. The baseline value is defined as the PSA level at the beginning of treatment phase 1 (Day 29 of study). The previous Phase II studies on 5-AZA and ATRA individually demonstrated their efficacy in delaying PSA rise among prostate cancer patients. Preclinical in-vivo study demonstrated that in adjuvant setting following primary tumor surgery, animals treated with the drug combination for 4 weeks have 73% reduction on the median cell count of disseminated tumor cells in lung comparing to control animals (Personal communications between [name] and [name]).

Thus, we assume the difference in progression free rates at end of the treatment periods between drug combination and no-therapy ranges between 30% to 60% and listed various scenarios of progression-free rates in Table 1. We use McNemar test statistic to calculate the range of sample size required to differentiate the treatment from no-therapy under each scenario. The maximum sample size is required when the PSA rise is independent in the two treatment periods for the same patient. The minimum sample size is required when the PSA progression status in the two treatment periods is highly concordant. With the planned 20 patients in total, we would have >80% power to detect the difference of PSA progression rate of 20% vs 60%, with two-sided type I error of 10%. All calculation was done using PASS software.

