### **8.4 Data analyses**

Analysis on efficacy and safety:

Patients will receive at least 8 weeks of treatment in order to be eligible for efficacy analysis. Patients who discontinued due to toxicity after 8 weeks of treatment will be included in efficacy analysis. Descriptive statistics such as mean/median/range and frequency will be provided for continuous and categorical variables separately, and the distributions of period baseline variables are contrasted between 5-AZA+ATRA and placebo using Wilcoxon statistics and Fisher's exact test statistics for continuous and categorical variables separately. Waterfall plot will be provided for PSA change relative to period baseline for all patients for each treatment arm and period. Analysis will follow the two-step procedure prescribed in for randomized crossover study for binary endpoint. To test for carryover effect, Wilcoxon rank-sum test stratified by prior PSADT will be performed to assess whether the sum of outcome variables from both periods is different between the randomization arms. If the test yields insignificant results, a similar test will be performed to compare the within-patient outcome difference between period 1 and 2 between the randomization arms to assess the treatment effect. If the carryover effect is significant, the primary analysis will be based on the progression free rates at the end of first treatment period using Chi-square test. In addition, general linear mixed model will be applied to assess the treatment effect, carryover effect, and period effect, adjusting for the stratification factor prior PSADT. The time to disease progression is defined as time to either PSA progression or radiographic progression whichever occurs first since discontinuation of ADT. Time to event endpoints will be summarized using Kaplan-Meier method. The time to event endpoints will be estimated using rank preserving failure time model (RPFTM) to obtain the counter-factual event times assuming cross-over did not occur (R package "rpfstm").

Descriptive summary will be provided for the safety endpoints. All patients who received at least one dose of study drug (treated set) will be included in the safety analysis.

Correlative analysis and biomarkers:

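### The default efficacy test uses only patients with outcomes in both phases, so a Phase 1 failure who leaves early drops out of it, and unequal leaving between the arms would bias the result

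*Combined protocol and SAP*

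**What the plan says.** Section 2.1 sets the primary comparison at the end of Treatment Phase 1. Section 8.4 analyses the trial as a crossover in two steps. A carryover test compares the sum of both periods' outcomes between arms. If it is not significant, "a similar test will be performed to compare the within-patient outcome difference between period 1 and 2 between the randomization arms to assess the treatment". Phase 1 alone becomes the primary analysis only if carryover is significant. A mixed model with treatment, carryover and period effects, adjusted for PSADT, is listed as an additional analysis.

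The sample size in Section 8.2 is also paired: "We use McNemar test statistic to calculate the range of sample size required". It concludes: "With the planned 20 patients in total, we would have >80% power to detect the difference of PSA progression rate of 20% vs 60"%. The level is 10%, two-sided. Each of the 20 patients counts as one complete pair.

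Three sets of rules decide who has a pair:

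- **Crossover (Section 3.1).** "During treatment phase 2, the 'no therapy' group will receive 5-AZA + ATRA on a 28-day cycle". Discontinuation events are those of Section 7.1, which lists illness, toxicity, withdrawal, noncompliance and investigator judgement, but not progression.
- **Follow Up Period (Section 7).** Patients are followed to 24 months from day 1 "unless there is evidence of radiographic progression and/or initiation of other cancer-directed therapies". Section 6.2 does not allow other anti-cancer therapy on study.
- **The 8-week rules.** Section 8.4 requires at least 8 weeks of treatment for the efficacy analysis. Section 8.2 replaces patients who did not complete 8 weeks of the combination. Section 8.3 enrols until 20 are evaluable and explains the margin to 30 by screen failures only.

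**The concern.** A patient with a Phase 1 outcome and no Phase 2 outcome has neither a sum nor a difference, and no section says how to score him. What happens to him depends on his arm:

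- **Drug-first, at least 8 weeks of drug.** He is eligible for the efficacy analysis but contributes nothing to the default test.
- **No-therapy-first.** He has had no drug, so the 8-week rules, read literally, exclude him and bring in a replacement.

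If those who leave are mainly Phase 1 failures, both routes remove failures and raise the Phase 1 progression-free rate among the patients kept. When the two arms lose failures at different rates, the treatment contrast shifts. Different rates are plausible. After a Phase 1 failure, a no-therapy-first patient is about to receive the study drug, while a drug-first patient has already had his course, and every patient entered with an indication for ADT. Starting other therapy at that point is foreseeable, and the restaging scans fall after three cycles, at the boundary between the phases.

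**Working it through.** **Inputs from the documents.** 20 patients, 1:1, so about 10 per sequence; two-sided 10%; 20% against 60%, read as progression-free rates without and with drug, as in the table in Section 8.2.

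**Assumed, because not given.** The share q of Phase 1 failures who leave before a Phase 2 outcome, varied by arm; independent periods.

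**Step 1: the plan's own figure.** McNemar, normal approximation, with difference d = 0.40. With independent periods the discordant share is 0.6×0.8 + 0.4×0.2 = 0.48 + 0.08 = 0.56; with full concordance it is 0.40.

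n = [1.645√pd + 0.842√(pd − d²)]² / d² gives 19.4 (independent) and 13.2 (concordant), against the stated 14–19. Power at 20 complete pairs with independent periods is Φ[(0.40√20 − 1.645√0.56)/√(0.56 − 0.16)] = 81%. The stated power is reproduced, provided all 20 pairs are complete.

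**Step 2: who could be exposed.** Expected Phase 1 failures are 10×0.8 = 8 no-therapy-first and 10×0.4 = 4 drug-first, so 12 of 20. This is an upper bound, because only those who leave are lost.

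**Step 3: bias.** In an arm with Phase 1 rate p, the share kept is k = p + (1 − p)(1 − q), and the rate among those kept is p/k. The estimated effect is half of [drug-first (Phase 1 − Phase 2)] − [no-therapy-first (Phase 1 − Phase 2)]. Replacing leavers with patients who stay does not change p/k.

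With no drug effect and p = 0.20 throughout:

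- 10% drug-first, 0% no-therapy-first: k = 0.92; (0.2174 − 0.20)/2 = 0.9 points.
- 20% and 0%: k = 0.84; (0.2381 − 0.20)/2 = 1.9 points.
- 50% and 0%: k = 0.60; (0.3333 − 0.20)/2 = 6.7 points.
- 75% and 25%: k = 0.40 and 0.80; (0.50 − 0.25)/2 = 12.5 points.

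Reverse case, true effect 40 points, 0% drug-first and 50% no-therapy-first: [(0.60 − 0.20) − (0.3333 − 0.60)]/2 = 33 points.

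**Step 4: error and power.** Simulation of the tie-corrected rank-sum test on within-patient differences, complete pairs only, unstratified. Ranges show the spread between runs and, for error, between replacing and not replacing leavers.

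| No drug effect: leaving, drug-first / no-therapy-first | Two-sided error | In favour of drug (nominal 5%) |
|---|---|---|
| 10–20% / 0% | about 10% | 6–7% |
| 50% / 0% | 13–14% | about 11% |
| 75% / 25% | 17–20% | about 17% |

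| True effect 40 points: leaving, drug-first / no-therapy-first | Pairs and power, leavers not replaced | Pairs and power, no-therapy-first leavers replaced |
|---|---|---|
| 0% / 0% | 20; 83% | 20; 83% |
| 25% / 25% | 20 − 3 = 17; 77% | 20 − 1 = 19; 82–83% |
| 50% / 50% | 20 − 6 = 14; 67–68% | 20 − 2 = 18; 79–80% |
| 0% / 50% | 20 − 4 = 16; 56–57% | 20; 67–70% |

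**The case against.** The strongest reply is that the plan may not send these patients off study at all. The sentence that ends follow-up at radiographic progression stands under Follow Up Period, and Section 3.1 puts follow-up after both phases. The Treatment Phase(s) text has no progression exit. Section 7.1 does not list progression and asks that patients who stop be followed per protocol. Section 8.4 plans PSA waterfall plots for all patients in each period. This stands as a limit on scope. A reader might infer that radiographic progression in Phase 1 removes a patient before Phase 2, but the documents do not establish it. They leave it ambiguous, since the Follow Up Period clock runs from day 1 of study.

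A reader might also infer that 12 of 20 patients will be lost. PSA-only progression is nowhere an exit trigger, and this is a PSA-recurrence population. Section 8.2 also words its scenario as a progression rate; taken literally, expected failures are 2 + 6 = 8.

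A third inference, that power generally falls below 80%, ignores the replacement rule. With no-therapy-first leavers replaced, equal leaving costs little.

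Finally, modest differences in leaving do little harm, and the planned mixed model could keep one-period patients. Both are true. But that model is only additional, states no missing-data assumption, and would still be fitted after the 8-week rule has excluded no-therapy-first leavers.

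**Conclusion.** The concern holds as a conditional one. The default test and its carryover pre-test select on Phase 1 outcome whenever Phase 1 failures leave before a Phase 2 outcome, and no rule in the plan repairs this. Replacement restores the number of pairs but not the comparability of the arms.

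The size depends on leaving rates that the documents do not give. Differences of 10–20 percentage points in leaving produce a false benefit of 1–2 points and error near the nominal 10%. A difference of 50 points produces 6–7 points, or 12–13 points when leaving is high in both arms (75% against 25%), with error of about 13% and 17–20%. In the reverse direction, a true 40-point effect is estimated at about 33 points, with power near 67–70% if leavers are replaced and about 57% if not. Leaving at equal rates with no drug effect does not bias the test. These figures assume 10 per sequence, independent periods and an unstratified test.

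**What to change.** 1. In Section 8.4, make the repeated-outcome model already planned there the treatment-effect analysis, in place of the test on complete differences. Specify it as a likelihood-based binary model with treatment, period and PSADT stratum, on every randomised patient with a Phase 1 outcome. For this analysis, drop the condition of 8 weeks of drug, and neither exclude nor substitute no-therapy-first patients who leave before Phase 2.
2. Beside it, report the Phase 1 progression-free comparison on all randomised patients with a Phase 1 outcome. This matches the objective in Section 2.1.
3. Reconcile Section 3.1, the Follow Up Period text and Section 7.1 on whether PSA and scan collection continues to the end of Phase 2 after progression in Phase 1.
4. State one scoring rule for a patient who starts other cancer-directed therapy during a period, and apply it consistently in the model.
5. State in Section 8.2 that the power above 80% assumes complete Phase 2 outcomes.

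The cost is SAP wording and a changed model specification, with no increase in the 20-patient target. The model assumes that missingness depends only on observed outcomes and arm. In a simulation check with no drug effect that kept all patients with a Phase 1 outcome, its bias was at most 0.2 points with independent periods, and 0.1–1.5 points with a latent within-patient correlation of 0.5 (4.7–9.1 points when incomplete pairs were dropped). That check did not cover type I error or power, so small-sample error at 20 patients should be simulated before the model is adopted. The model as specified here has no carryover term, so the plan should say how carryover will be examined.

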### **8.3 Randomization Schema**

Since prior PSA doubling time is a known prognostic factor to disease progression, the randomization will be stratified on PSA doubling time: PSADT $\leq$ 3 months vs PSADT>3 months. A stratified block randomization of block size 1 will be used and separate randomization lists are generated in different strata (See appendix). The enrollment will continue until total number of 20 evaluable patients is reached. The target accrual number is set at 30 to account for screen failures. The maximum imbalance in each stratum is 1 and maximum total imbalance across strata is 2.

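### The fallback chi-square in 8.4 ignores the PSADT strata used in randomisation, which makes it conservative and costs a little power; a stratified CMH test would match the design

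*Combined protocol and SAP*

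**What the plan says.** Section 8.3 gives the reason for stratifying: "Since prior PSA doubling time is a known prognostic factor to disease progression, the randomization will be stratified on PSA doubling time". The cut is at 3 months (<=3 vs >3), and the imbalance within a stratum is limited to 1 patient.

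Section 8.4 then sets out a two-step crossover analysis. The carryover test is a Wilcoxon rank-sum test stratified by prior PSADT. If it is not significant, the treatment effect is assessed with a test described as similar, which I read as stratified too. If it is significant, "the primary analysis will be based on the progression free rates at the end of first treatment period using Chi-square test". That sentence names no stratification, continuity correction or exact version. A mixed model adjusting for PSADT is planned in addition, but it is not the primary test.

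Section 8.2 bases the sample size on a paired comparison: "We use McNemar test statistic to calculate the range of sample size required to differentiate the treatment from no-therapy under each scenario". It claims more than 80% power for 20% vs 60% at a two-sided 10% level, "With the planned 20 patients in total". No power is given for the fallback comparison.

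**The concern.** A test that ignores a prognostic factor balanced by design uses too large a variance. The between-stratum variation stays in the variance of the statistic, although the randomisation has removed it from the difference between arms. The test then rejects less often than its nominal level, and it loses some power.

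The omission is also inconsistent within one paragraph: the other tests and the mixed model account for PSADT, and only this one does not. The branch is conditional, but when it applies it carries the primary conclusion. It is also the only named test in 8.4 that directly compares the arms on the stated primary endpoint, the progression-free rate at the end of Treatment Phase 1. A reader could also assume that the >80% power in 8.2 covers this branch.

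**Working it through.** **Inputs from the documents.** 20 evaluable patients (8.2), allocated 1:1 (3.1), so about 10 per arm; two-sided alpha 10%; 20% vs 60% (8.2); PSADT strata <=3 vs >3 months, nearly balanced (8.3).

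**Assumptions, because the documents give no figures.** Stratum sizes of 5+5 per arm (3+7 as a check); the stratum rates shown below; and, for power, a common odds ratio across strata that brings the treated average to 60%. I take 20% and 60% as progression-free rates. Reading them as progression rates only swaps the two outcome labels and leaves the power unchanged.

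**Step 1: the plan's own figure.** McNemar, normal approximation:

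N = [1.645·√pd + 0.842·√(pd − d²)]² / d², with d = 0.40.

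- Maximal concordance, pd = 0.40: N = 13.2.
- Independence, pd = 0.2×0.4 + 0.8×0.6 = 0.56: N = 19.4.

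Rounded up this is 14–20, against 14–19 in the sample-size table. Power at N = 20 is 81.1% (independence) to 93.7% (concordance). The >80% claim is reproduced for the paired comparison.

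**Step 2: power of the fallback.** With 10 per arm, rates 0.2 and 0.6, and mean 0.4:

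power = Φ{[0.4·√10 − 1.645·√(2×0.4×0.6)] / √(0.16 + 0.24)} = 57.9%.

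Exact enumeration of the Pearson chi-square gives 61.4%. With the Yates correction or Fisher's test it is 42.5%. By the formula, 80% power needs (1.645·√0.48 + 0.842·√0.40)² / 0.16 = 17.5, so 18 per arm.

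**Step 3: why ignoring the strata is conservative.** Compare the average within-stratum variance with the pooled variance under the null:

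- 20%/60%: (0.16 + 0.24)/2 = 0.20 against 0.4×0.6 = 0.24, ratio 0.83.
- 10%/70%: (0.09 + 0.21)/2 = 0.15 against 0.24, ratio 0.63.

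The chi-square divides by the larger variance, so its true size falls below 10%.

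**Step 4: exact enumeration of both tests.** Let a and c be the numbers progression-free in the two arms, and t = a + c.

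- Pearson: 20(a − c)² / [t(20 − t)].
- CMH without continuity correction, n_k per arm in stratum k: [Σ(a_k − t_k/2)]² / Σ{t_k(2n_k − t_k) / [4(2n_k − 1)]}.

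Both are compared with 2.706. The last column is the conditional exact stratified test. Strata are 5+5 per arm.

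| Scenario | Chi-square | Asymptotic CMH | Exact stratified |
|---|---|---|---|
| Power, control 20%/20% | 61.4% | 61.5% | 42.7% |
| Power, control 10%/30% | 61.6% | 62.9% | 43.7% |
| Power, control 5%/35% | 62.0% | 66.9% | 47.6% |
| Size, null 40%/40% | 11.0% | 11.1% | 4.1% |
| Size, null 50%/50% | 11.6% | 11.6% | 4.3% |
| Size, null 20%/60% | 7.8% | 9.7% | 3.4% |
| Size, null 10%/70% | 4.1% | 8.9% | 2.6% |

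With strata of 3+7, the chi-square and CMH sizes are 8.9% and 9.7% at 20%/60%, and 5.7% and 8.7% at 10%/70%.

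**Step 5: how strong must PSADT be?** Over both stratum splits, with a 20% average control rate, CMH gains about 0–2.5 points of power up to a stratum odds ratio of 6, and about 1–9 points at odds ratios of 10–20.

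**The case against.** The strongest reply is that this is a small matter. The chi-square applies only if carryover is significant, a PSADT-adjusted mixed model is planned as well, and at moderate prognostic strength the power difference is 1 or 2 points. All of that stands, and it limits the weight of the point. It does not justify the omission: the mixed model is not the primary test, and nothing in the documents explains why this one test drops the strata.

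Three stronger readings are tempting, and the documents do not support them.

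- **Missing stratification explains the low power of the fallback.** It does not. The fall from >80% to about 61% comes from replacing a paired comparison with a single-period comparison of about 10 per arm. A dramatic stratification loss needs an extreme scenario. Control rates of 2%/50% give 47% power unstratified and 64% with CMH, but they imply an odds ratio of (0.50/0.50)/(0.02/0.98) = 49 and an average control rate of 26%. Without any strata, 26% vs 60% already has only 49% power.
- **Ignoring the strata raises the false-positive rate.** The effect goes the other way. The excess over 10%, at most 11.6%, is discreteness, and the asymptotic CMH test shares it. Choosing the test by a carryover pre-test, whose level the plan does not state, is a separate issue. With that level assumed at 10%, simulated overall error is about 11–16% with either fallback.
- **An exact stratified p-value would be the safer choice.** It would be more conservative than the test it replaces, as the last column of the table shows.

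**Conclusion.** The point holds as a modest mismatch between design and analysis. The fallback primary test ignores strata that 8.3 calls prognostic and that the carryover test in 8.4 uses. If PSADT is prognostic, the chi-square runs below its nominal 10% (7.8% at null rates 20%/60%, 4.1% at 10%/70%), while the asymptotic CMH test stays nearer to it (9.7% and 8.9%). The power given up is nil without a PSADT effect, about 1 point at control rates of 10%/30% and about 5 points at 5%/35%. It is larger only if PSADT is very strongly prognostic.

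These figures rest on 10 per arm, strata balanced between arms, and assumed stratum rates and sizes. The direction does not depend on the particular rates: in every scenario examined, CMH had at least the power of the chi-square, and its size was closer to 10% whenever the strata differed.

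Separately, 8.2 gives no power for this branch. It is about 61% for 20% vs 60%, and the >80% figure should not be read as covering it.

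**What to change.** In 8.4, replace the chi-square wording with an asymptotic Cochran-Mantel-Haenszel test stratified by PSADT (<=3 vs >3 months), without continuity correction, at the two-sided 10% level. Report a stratified risk difference with a 90% CI. Do not require a conditional exact p-value: it would cut power to about 43–48% and true size to about 2–4%.

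In 8.2 or 8.4, state that this between-patient comparison of about 10 per arm has about 61% power for 20% vs 60%, and that the >80% applies only to the paired McNemar comparison.

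The cost is a sentence or two of wording, with no new data and no change in sample size. The downside is that the asymptotic CMH test can still run slightly above 10%, up to about 11.6%, as the chi-square does. The change does not restore the power lost by using one period, and it does not address any error inflation from the carryover pre-test.

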### 1.2 Rationale

Our long-term goal is to target the biology of dormant PCa DTCs to prevent relapse of clinical disease. In pre-clinical models, specific micro-environmental cues have been shown to activate a transcription factor (TF) network, which drives epigenetic programs of quiescence and survival in dormant tumor cells. Specifically, ATRA could induce a high p38/ERK activity ratio and dormancy in previously proliferative DTCs through TGF $\beta$ 2 signaling in the BM and through upregulation of BMP7. The p38 activation also induces TFs DEC2 and NR2F1 to induce a dormant state. Overall, the dormancy TF network serves as a signature to predict longer metastasis-free periods and to identify dormant DTCs recovered from BM of prostate cancer patients. Interestingly, many dormancy genes are epigenetically silenced and can be re-expressed using a short-term pulse of low dose 5-AZA, a DNA methylating agent and DNMT1 inhibitor. When we introduced 5-AZA and ATRA in malignant prostate cancer cell lines for three days, many cells displayed upregulation of dormancy biomarkers and the response was maintained for at least 2 weeks.

Our pre-clinical work led us to design a “reprogramming therapy” combining two available FDA-approved drugs (5-AZA, ATRA) to reprogram proliferative cells into stable induced dormant cancer cells (iDCCs). Prior studies with the drugs of interest were performed in castration-sensitive PCa patients with prior exposure to ADT and with fast PSA doubling time (PSADT). We will test if 5-AZA+ATRA extends the progression-free period and delays biochemical and clinical recurrence via induction of PCa cell dormancy. This study will allow us to temporally understand the impact of the reprogramming therapy on the delay in chemical and clinical progression, and to correlate clinical activity with biomarkers of dormancy in DTCs.

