### 2.2 Secondary Objectives

The secondary objectives are:

- To compare time to disease progression from start of Treatment Phase 1 during the 24-month study period between 5-AZA+ATRA and no-therapy.
- To correlate antitumor activity and progression with biomarkers of dormancy in BM aspirates and peripheral blood.

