**Table 1. Therapeutic agents: Dosing and administration schedule**

Agent	Dose	Route	Schedule	Cycle Length
5-AZA	40 mg/m 	SQ	Days 1-5 x 12 weeks	4 weeks (28 days)
ATRA	45 mg/m  daily (divided into 2 doses)	PO	Days 3-7 x 12 weeks	

*Note: Height and weight will be obtained at Day 1 of each treatment cycle to determine treatment dosing.*

The daily dosing for ATRA will be rounded to the nearest 10 mg increment and given in two divided doses per day.

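### The 24-month comparison with no-therapy rests on a rank preserving failure time model whose exposure coding and effect duration the plan does not state, although no-therapy is observed for only 12 weeks

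*Combined protocol and SAP*

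**What the plan says.** The secondary objective in section 2.2 is "To compare time to disease progression from start of Treatment Phase 1 during the 24-month study period between 5-AZA+ATRA and no-therapy".

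Section 3.1 sets the exposure. From Day 29 the treated arm "will receive treatment on a 28-day cycle, in the absence of prohibitive toxicities, for 3 cycles", which the dosing table in section 5 gives for 5-AZA as "Days 1-5 x 12 weeks". Then "During treatment phase 2, the 'no therapy' group will receive 5-AZA + ATRA on a 28-day cycle". This is not conditional on progression, and no washout is stated. Afterwards "all patients will be followed for a total of 24 months from the start of the study".

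For time to event, section 8.4 says "Time to event endpoints will be summarized using Kaplan-Meier method", and that these endpoints will be "estimated using rank preserving failure time model (RPFTM) to obtain the counter-factual event times assuming cross-over did not occur". It names no log-rank, Cox or other as-randomised comparison. It does not say how exposure is coded once a patient stops drug, whether the effect is taken to last, how re-censoring is done, or what happens if the model has no solution. Section 8.4 counts time from discontinuation of ADT, whereas section 2.2 counts it from the start of Treatment Phase 1.

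**The concern.** A rank preserving failure time model is normally used when some controls switch to a treatment that the other arm stays on. Here the whole control group is scheduled to start at week 12, when the treated arm stops. Drug and no drug are contrasted as randomised for 12 weeks. The roles reverse for the next 12, and from week 24 both arms have been scheduled the same 12 weeks of drug. Most of a 24-month no-therapy curve would therefore come from the model. If its unstated settings drive the answer, the reported effect on this objective reflects an analyst's choice that the data can hardly check.

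**Working it through.** **Inputs.** 20 patients randomised 1:1, so 10 per arm (3.1, 8.2). Drug in weeks 0-12 or weeks 12-24, counted from Day 29. Follow-up is 24 months from Day 1, about 104 - 4 = 100 weeks from Day 29. The 20% vs 60% rates and the two-sided 10% level come from 8.2. Exponential event times are an assumption.

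**The plan's own figure.** Section 8.2 sizes only the primary endpoint, by McNemar's test: n = (1.645√D + 0.842√(D - d²))²/d², with d = 0.4.
- Independent periods: D = 0.2×0.4 + 0.6×0.8 = 0.56, so n = (1.231 + 0.532)²/0.16 = 19.4, rounded up to 20.
- Fully concordant periods: D = 0.4, so n = (1.040 + 0.412)²/0.16 = 13.2, rounded up to 14.

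The plan gives 14-19. Power with 20 patients is 81% to 94%, so the claim of more than 80% reproduces. Nothing is sized for time to progression.

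**What the model can learn.** The model sets U = T_off + exp(psi)·T_on, where U is the event time without drug.
- *On-drug coding.* A treated-arm event at T > 12 gives U = (T - 12) + 12·exp(psi). A control event at T > 24 gives the same expression. Events after week 24 shift equally in both arms and say little about psi.
- *Ever-treated coding.* The treated arm has U = exp(psi)·T. Controls with T > 12 have U = 12 + exp(psi)·(T - 12). Later events now count, but only by assuming that the effect never ends.

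**True effect.** Hazards are -ln(0.2)/12 = 0.134 and -ln(0.6)/12 = 0.0426 per week. The ratio is 0.317, so psi = ln(0.317) = -1.15.

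**Simulation.** 1,000 trials per case, inverting the log-rank test over psi from -6 to 6. A limit is called missing if none is found in that range. Limits are 95% and re-censoring is at min(C, C·exp(psi)) unless stated.

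| Coding | True effect | Median psi (true -1.15) | Limit missing | Coverage |
|---|---|---|---|---|
| Ever-treated | lasts | -1.20 | 0.2% | 92% |
| On-drug | ends at stop | -1.32 | 42% | 93% |
| On-drug | lasts | -2.64 | 47% | 82% |
| Ever-treated | ends at stop | -0.60 | 0.1% | 79% |

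For on-drug coding with an effect that ends at stop, the missing share depends on the settings:
- Re-censoring as in the table: 42% (95% limits) or 27% (90% limits).
- Re-censoring on the 12-week maximum exposure: 81% or 71%. The median is then -0.96 with 95% limits, and there is no point estimate in 18% of trials.

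As acceleration factors, exp(-0.60) = 0.55 and exp(-2.64) = 0.07, against a true 0.32.

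**Other reading of the rates.** Section 8.2 words 20% vs 60% as progression rates. Read that way (40% vs 80% progression-free, true psi -1.41), the pattern is the same. Ever-treated coding with a lasting effect gives median -1.50 with 7% missing. The others give 87-93% missing, median -2.94, and median -0.42.

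**Log-rank power, two-sided 10%.**
- Stopped at week 12: expected events are 10×0.8 + 10×0.4 = 12. Schoenfeld power is Φ(√(12/4)×1.15 - 1.645) = Φ(0.34) = 63%; simulation gives 60-63%.
- Over 24 months: about 32% (effect ends at stop) to 52% (effect lasts).
- For 30% vs 60%: about 38-42% at week 12 against 21-34% over 24 months.

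**The case against.** A reader might infer that the failure time estimate would usually be unbounded or biased. The documents do not support that. They fix no exposure coding, and ever-treated coding with a lasting effect, the combination nearest the stable-dormancy hypothesis of section 1.2, is bounded and nearly unbiased. With correctly specified on-drug coding, median bias is modest. What goes missing is mainly a confidence limit, less often the estimate, and how often depends on re-censoring and confidence level.

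Nor is control crossover the main cause. At the planned rates only about 2 of 10 controls are event-free at week 12. The treated arm's stop and 10 patients per arm matter more.

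The plan states no test, alpha or power for this endpoint, which is secondary in a pilot, so comparing powers ranks two weak tests. The 12-week log-rank also largely repeats the primary window: for 20% vs 60% its power is 63%, against 61% for the first-period Chi-square that 8.4 already holds in reserve. Its power also depends on counting week-12 rises that are confirmed later; losing them lowers it to 55%.

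These limits stand, but they do not rescue the plan as written. It does not choose the combination that works, and the only persistence it reports for the two drugs together is at least 2 weeks in cell lines. A lasting effect would also be carryover, which undermines the within-patient comparison that 8.4 prefers for the primary endpoint. The carryover test and mixed model there offer only partial cover, since that procedure is set out for the binary endpoint.

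**Conclusion.** The point holds in this form: after week 12 the no-therapy comparison is built by a model whose decisive settings are unstated and which the design can hardly check. One of four combinations of coding and true effect works. The other three leave limits missing in 27% to 81% of trials, give median psi -2.64 with 47% missing, or give median psi -0.60 with 79% coverage, against a true -1.15. A log-rank test stopped at week 12 needs none of these assumptions and has about 60-63% power, against about 32-52% over 24 months.

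The figures assume exponential times, a common effect whenever drug is given, full adherence and all 20 patients analysed as randomised (8.4 instead requires at least 8 weeks of treatment for the efficacy analysis). The missing-limit shares also depend on the search range: the 42% becomes 64% when psi is searched only from -4 to 4. Assigning events to scheduled visits changes the power little (62-63% against 35-52%). This should be changed, but it does not touch the primary endpoint.

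**What to change.** In section 8.4:

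- Make the between-arm analysis a PSADT-stratified log-rank test, with hazard ratio and 90% confidence interval, from Day 29 and censored at the start of Treatment Phase 2.
- Count a PSA rise first seen by the week-12 visit as an event at that visit if it is later confirmed. Count the end-of-Phase-1 scan as Phase 1.
- Present the 24-month Kaplan-Meier curves as immediate versus 12-week-deferred therapy.
- Keep the failure time model as a sensitivity analysis under both exposure codings, with the re-censoring rule and a rule for no solution stated.
- Align the time origin with section 2.2.

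Reword section 2.2 to match.

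The cost is text only, with no added patients or visits. The trial would no longer claim a 24-month comparison with no therapy. The 12-week test covers the same window as the primary endpoint, adds little power beyond it and remains underpowered.
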